SBP	Systolic Blood Pressure
SNNPR	Southern Nations Nationalities and Peoples Region.

III. Executive Summary

Background: Long-term use of opioids has been linked to various side effects and decreased patient satisfaction after anesthesia. A combination of drugs with opioid was used for intraoperative analgesia. Multiple drugs, by avoiding opioids, was a new opinion suggested. Opioid-free anesthesia with a combination of drugs is a new idea to avoid opioid from postoperative analgesia.

Objective: To determine the effectiveness of low-dose ketamine and intravenous lidocaine versus fentanyl for postoperative pain in patients undergoing elective gynecologic surgery under general anesthesia at Dilla University Teaching Hospital and Hawassa University Comprehensive and Specialized Hospital from April 10 to October 10, 2023.

Methodology: A multicenter, randomized, controlled, single-blinded superiority trial will be conducted with 70 adult patients undergoing elective gynecologic surgery under general anesthesia. Randomization will be done by a computer-generated random allocation sequence in equal ratios to the treatment group ($T = 35$) and the control group ($C = 35$). The primary dependent variable is the pain severity measured by a visual analog scale postoperatively at discharge from the post-anesthesia care unit, 6th hour, 12th hour, and 24th hour, and the secondary outcomes are postoperative nausea and vomiting, postoperative analgesia request, and intraoperative cardiac adverse events. Student's t-test, analysis of variance, and chi-square test will be used for data analysis. A p-value of less than 0.05 was determined as statistically significant.

Work plan and budgeting: - study will be conducted from April 10, 2023, to October 10, 2023, with a cost of 41625 ETB.

1. Introduction

1.1. Background

Surgical procedures that are performed based on the underlying cause and the specific needs of the patient result in nociception, which is mediated by pathways through the nervous system with the interplay of various factors involved in the experience of pain. Two-thirds of patients who underwent surgery reported moderate to severe postoperative pain. To reduce the effects and promote a speedy recovery, surgical pain management techniques were urged to cover both non-pharmacological and medication-based therapies([1-4](#)).

According to evidence, fewer than half of people who undergo surgery report satisfactory pain alleviation. Inadequate pain control and the use of unmodified techniques harm the quality of life, function, and functional recovery of patients who underwent surgery. The perioperative anesthesia handling and thorough consideration of medications administered to a surgical patient have been applied([3](#)).

Opioids are commonly used medications to treat perioperative pain for a long period. They have been used as anti-nociceptive, decreasing alertness, and reducing the amount of centrally acting anesthetics([5](#)). They had also been administered to decrease blood pressure during laryngoscopy and intubation and suppress airway reflexes during airway manipulation. However, opioid usage has been linked to a variety of adverse effects such as postoperative ileus, constipation, postoperative nausea and vomiting (PONV), and opposite effects including opioid-induced pain modulation and tolerance([6, 7](#))

A shift of pain management strategies with the implementation of less invasive surgical techniques and the advancement of anesthesia management has been implemented. Drugs that aim at different nociceptive receptors have been discovered and applied in perioperative patient care. Multimodal analgesia, which combines both opioids and opioid-free analgesics to avoid the negative consequences of using opioids alone, has been employed ([1, 8](#)). However, the issue of pain enhancement and opioid-related adverse events has not been fully resolved and has been reported with the technique of multimodal anesthesia ([9, 10](#)).

Opioid-free anesthesia (OFA) involving a combination of drugs and techniques was suggested to avoid opioids from intraoperative analgesia. It was intended to avoid opioid from the postoperative analgesia regimen but was later taken as a viable and optional method for perioperative anesthesia management([11](#), [12](#)). Individual medications such as N-methyl-D-aspartate (NMDA) antagonists, sodium channel blockers, anti-inflammatory drugs, and alpha-2 agonists are being administered for analgesia. They aimed to reduce the reduction of MAC of volatile anesthetics, avoiding negative effects associated with opiates, and providing greater patient satisfaction after surgery when used in combination ([13-18](#)).

Intravenous lidocaine in doses less than 2mg/kg is reported to relieve pain by blocking sodium channels in both the peripheral and central nervous systems. It was also thought to reduce central and deafferentation pain and aid in wound healing. At lower doses up to 1 mg/kg, ketamine can provide significant pain relief without negative effects by eliminating opioid tolerance and having anti-hyperalgesic effects. A combination of intravenous (IV) lidocaine and low-dose ketamine can be used for intraoperative analgesia without adverse effects, even though it has not been routinely used for intraoperative anesthesia.

1.1. Problem statement

The increased utilization of opioids has raised worries and disapproval about the customary practice of opioid administration for anesthesia. A study by Chan et al([19](#)) in Canada reported that about 73% of patients undergoing major surgery and 66.7% of patients undergoing intermediate procedures were using perioperative opioid. It is reported that approximately 11% of patients who undergo surgery with opioid anesthesia experience moderate to severe adverse effects related to opioids([20](#)). Patients given perioperative opioids were associated with risks including a doubled likelihood of inpatient mortality, a 30% rate of readmission within a month, 55% longer hospital stays, and tripled hospitalization costs, which highlight the urgent need for effective solutions to the problem ([20-23](#)).

Both OFA and OBA acknowledge the pain-relieving abilities of opioids but also note that opioid can lead to increased pain sensation after surgery and an increased need for analgesics([24](#), [25](#)). According to the nationwide survey in the US([26](#)), the occurrence of pain was 84% postoperatively in general surgical patients, and 74% of patients who underwent major surgery reported debilitating pain at immediate postoperatively hours. A study in Europe by Buvanendran et al([27](#)) reported that greater than 50% of gynecologic surgical patients experience substantial to extreme postoperative pain up to discharge from the hospital, which was mainly associated with the intraoperative use of opioids.

A study by R. Park et al([28](#)) in Europe reported the occurrence of severe pain after gynecologic surgery was 32% within 24 hours postoperatively, which was mainly associated with poor pain management at immediate discharge. A study by Anberbir et al([29](#)) at Addis Ababa reported that about 73% of gynecologic surgical patients experience moderate to severe pain more than once within 24 hours postoperatively. Preoperative anxiety, urban dwellings, and being uneducated were the reported reasons for pain severity.

Though the literature on OFA technique in procedures such as laparoscopic cholecystectomy, gynecologic, and bariatric surgery has shown its advantages([4](#), [25](#), [30](#)), certain scholars have reported inconclusive and contesting results ([31-33](#)). The postoperative opioid-free anesthesia (POFA) trial, which was the most comprehensive and current multicenter trial, was stopped due to safety concerns after a few patients developed severe bradycardia([24](#)).

The majority of the research is constrained to certain surgical procedures and is carried out in settings with modern facilities; however, a paucity of literature on the subject. Additionally, most of the studies done on OFA are carried out in Europe and Asia, and there are the fewest studies in Africa ([19\(4\)](#)).

Despite the reported surgeries under OFA techniques were being reported with better profiles, the effectiveness of the technique has not been well established. Contrasting research results and lack of relevant literature in resource-constrained environments made the implementation of the OFA idea challenging and indeterminate. Nevertheless, more research is required to address the issue in the resource desiccated settings like our country. The purpose of this trial is to compare the effectiveness of low-dose ketamine and intravenous lidocaine for postoperative pain compared with fentanyl for patients undergoing gynecologic surgery under general anesthesia.

1.2. Significance of the study

Even though the OFA concept remained doubtful of its validity and feasibility, reducing opioid-related harm in surgical patients improves the patient's postoperative recovery. The calamities associated with opioid-based anesthesia are obvious and need to be solved. Some works of literature on the OFA principle have reported improved postoperative recovery, and others reported comparable results and drug-related side effects. Additional studies will narrow these gaps within the findings.

Gynecologic surgery carrying a risk of postoperative nausea and vomiting, as well as moderate to severe discomfort, can benefit from avoiding the use of opioid-based anesthesia techniques. This can decrease unwanted opioid effects, higher costs, longer hospital stays, higher postoperative pain scores, and can increase postoperative patient satisfaction.

Two recent RCTs conducted in Cameroon and Egypt have shown promising results using the OFA protocol without dexmedetomidine, which could lead to the adoption of the OFA technique in resource-limited settings. In works of literature on OFA in resourceful settings, drugs like ketamine, lidocaine, NSAIDs, and others, can open the eyes of investigators covered in dexmedetomidine's fancy, especially for resource-depleted settings.

This single-blinded prospective randomized controlled trial aimed to determine the effectiveness of OFA with low-dose ketamine and intravenous lidocaine vs. general anesthesia with fentanyl for postoperative pain in patients undergoing elective gynecologic surgery under general anesthesia. Due to the lack of comparable studies on the subject, the outcome of the study can lead to a quick pace for patient management and is acceptable in the scientific environment preferred by scientific literature.

2. Literature review

A growing body of knowledge has described the potential adverse effects of opioid analgesics, and the latest calamity, the "opioid crisis," needs keen emphasis. To overcome the associated calamity, works of literature urged the practice of giving up on opioids and the use of other modalities for pain pharmacotherapy([8](#), [20](#)). OFA is one of the modalities, and the most recent and toothsome works of literature are in developed countries, so the idea quickly improved, but the lack of the saint drug held back the idea in the developing world([5](#), [34](#)).

2.1. Perspectives on OFA and opioid-based anesthesia

Helene Beloeil, in the narrative review, described OFA as a rationale that aimed to avoid the intraoperative use of opioid analgesics. He urged that the intraoperative use of opioids is associated with an increase in postoperative pain scores by worsening the sensitization of injured tissue during surgery. OFA using a combination of modalities and drugs, including NMDA receptor inhibitors, anti-inflammatory drugs, Na⁺ channel blockers, and 2-agonists, was documented at decreasing doses of individual drugs by avoiding the side effects associated with specific drugs ([35](#)).

The American Society for Enhanced Recovery and Perioperative Quality's joint consensus statement in 2020 proposed the suitability of OFA techniques and praised the findings of existing works in the literature, but questioned the availability of significant data on the benefits and harms of the strategy. They advocated the feasibility of the OFA technique in terms of reduced recovery room time, decreased PONV, reduced analgesic requirements, and a decreased postoperative pain scale([36](#)). An article from the American Anesthesiology described OFA as a "fashion" that they termed a campaign aimed at eradicating opioid from use as a pain medication ([37](#)).

2.2. Opioid-related adverse events between OFA and OBA

In the systematic review and meta-analysis of five RCTs on the intraoperative use of OFA vs. conventional GA on adult patients undergoing non-cardiac surgery, Frauenknecht et al. reported a 20% reduction in PONV with a CI of 0.77 (0.61–0.9) and a P value of 0.03 in the OFA group. They documented the association of delayed recuperation, a higher hospital stay, and increased medical costs with patients given opioid anesthesia([25](#)).

An RCT by Feng et al([38](#)) on 120 adult patients undergoing thoracoscopic lung resection compared the incidence of PONV with patients undergoing anesthesia under OFA with ketamine and dexmedetomidine and OBA with sufentanil. They reported the occurrence of PONV in the OBA group, which was twice as much as the PONV in the OFA group (15% vs. 31.7%), OR = 0.38, at 95% CI (0.16-0.91), and a p-value of 0.031 at 24 hours postoperatively.

Massoth et al([32](#)) conducted an RCT comparing the occurrence of PONV in 152 women undergoing gynecological surgery by OFA using dexmedetomidine and ketamine with conventional GA with sufentanil. They reported no significant difference in the occurrence of PONV (71.4% in the opioid-based anesthesia group vs. 70.5% in the OFA group, with a p-value of 0.91), vomiting or antiemetic requirements (8.1% vs. 10.5%) with a p-value of 0.57, and the occurrence of adverse effects at 24 hours postoperative.

The large-scale retrospective cohort study on data of 521 patients who underwent laparoscopic hysterectomy by Forget et al([39](#)) reported comparable outcomes in the occurrence of nausea (10% vs. 7%) and vomiting (2% vs. 1%) with p-values of 0.21 and 0.3, respectively, in the patient groups receiving OBA and OFA. The study was conducted on the data of 118 patients who received OFA with clonidine and ketamine, and 403 patients given OBA with sufentanyl.

2.3. Severity of postoperative pain

In a systematic review and meta-analysis of 11 RCTs comparing OFA and standard GA with opioid on laparoscopic, gynecological, and abdominal surgeries, Olausson et al. reported significantly lower postoperative analgesic consumption in the OFA group (-6.0 mg with a p-value of 0.00001). They also documented decreased adverse effects of opioids (0.32, I² = 56%, and p-value of 0.00001), while no significant difference in GI symptoms, shivering, and postoperative hypoxemia between the two groups ([40](#)).

Unlike Olausson et al.'s, Frauenknecht et al.'s meta-analysis of 5 RCTs on OFA vs. conventional GA with opioids found a non-significant difference in postoperative pain scores; a p = 0.38 difference between the two groups. They noted that the short duration of action of remifentanil, which most works of literature they reviewed used, may have affected the outcome of the postoperative pain score ([25](#)).

A randomized placebo-controlled trial done by Kang et al. on 168 female patients undergoing breast surgery in Japan with the OFA group given ketamine 0.5 mg/kg vs. the placebo group has documented a lower postoperative pain scale in patients receiving ketamine (69.0% vs. 86.9% with $P = 0.005$ at 3 months) (15) in the patients received OFA.

An RCT on OFA vs. OBA by Torchier et al(30) on 36 patients without dexmedetomidine for gynecologic surgeries, including breast surgery, documented a higher postoperative pain scale (reported by the NRS) in patients receiving opioids at 24 hr. and 48 hr. They also reported a 100% success rate of intraoperative opioid-free anesthesia with ketamine 0.5 kg/mg followed by infusion, and lidocaine 1.5 mg/kg bolus, followed by infusion.

2.4. The effectiveness of drugs used in OFA

Wang et al., in the review of 12 randomized controlled studies comprising about 900 patients undergoing different surgical procedures under GA, compared s-ketamine in bolus doses of 0.075 to 0.5 mg/kg and infusions from 1.25 to 10 μ g/kg/min with placebo. They recorded better pain scores at rest up to 24 hours in patients given ketamine and similar pain scores at 48 hours postoperatively ($p = 0.53$) in both ketamine and placebo(41).

In another meta-analysis of nine randomized controlled trials comparing IV ketamine with placebo for adult surgical patients on opioid use, Forget et al also documented a significant decrease in postoperative pain scale at 24 hours in patients taking ketamine, with a mean difference of -0.79. About a 97 mg and 186 mg decrease in opiate consumption at 24 and 48 hours, respectively, were documented in patients taking ketamine (16).

In the review of recent works of literature on subanesthetic doses of ketamine for intraoperative pain and up to 48-hour postoperative administration, Jouguelet et al. reported a reduction of postoperative pain score and up to 40% reduction of postoperative analgesic consumption by bolus then continuous infusions given of up to 1.2 mg/kg/h or 1.3 mg/kg ketamine doses, respectively. On subanesthetic ketamine use, and reported that ketamine, when used in a subanesthetic dose, has no documented associated adverse events (42).

Touchier et al. performed an RCT by using lidocaine with ketamine on 36 gynecologic patients without dexmedetomidine and reported better hemodynamic stability in the OFA group ($p = 0.0026$) compared to opioid-based anesthesia with remifentanil (30).

Foo et al., in the statement on the efficacy and safety of lidocaine, described the analgesic, anti-hyperalgesic, and anti-inflammatory effects of lidocaine from its actions on muscarinic and NMDA receptors. They recommended 1–2 mg/kg as an initial bolus followed by a continuous infusion of 0.5–3 mg/kg/hr. Avoiding a dose greater than or equal to 3 mg/kg/hr, and avoiding lidocaine in patients with hepatic or renal impairment. Lidocaine should not be used on patients whose weight is less than 40 kg([12](#)).

3.1. General objective

To determine the effectiveness of low-dose ketamine and intravenous lidocaine vs. Fentanyl for postoperative pain in adult patients who underwent elective gynecologic surgery under general anesthesia at Dilla University Teaching Hospital and Hawassa University Comprehensive and Specialized Hospital from April 10, 2023, to October 10, 2023

3.2. Specific objectives

To compare the postoperative pain severity between groups of adult patients who underwent elective gynecologic surgery under general anesthesia at Dilla University Teaching Hospital and Hawassa University Comprehensive and Specialized Hospital from April 10 to October 10, 2023

To compare postoperative analgesic requests between groups of adult patients who underwent elective gynecologic surgery under general anesthesia at Dilla University General and Teaching Hospital and Hawassa University Comprehensive and Specialized Hospital from April 10 to October 10, 2023

To compare the occurrence of PONV between groups of adult patients undergoing elective gynecologic surgery under general anesthesia at Dilla University Teaching Hospital and Hawassa University Comprehensive and Specialized Hospital from April 10 to October 10, 2023

To compare the occurrence of intraoperative cardiac adverse events for adult patients undergoing elective gynecologic surgery under general anesthesia at Dilla University Teaching Hospital and Hawassa University Comprehensive and Specialized Hospital from April 10 to October 10, 2023

4. Methodology and materials

4.1. Study area and period

The research will be carried out at Dilla University General and Teaching Hospital in Gedio Zone, and Hawassa University Comprehensive and Specialized Hospital in Hawassa, SNNPR Ethiopia, from April 10, 2023, to October 10, 2023.

Dilla University General and Teaching Hospital is located in the administrative center of the Gedeo Zone, SNNPR, on the main road, 372 km from Addis Ababa to Nairobi. Dilla University General and Teaching Hospital is in the southern part of town, on the main road to Moyale. The hospital has about eight specialty departments, such as anesthesiology, surgery, obstetrics and gynecology, internal medicine, and pediatrics.

The general and teaching hospital has one OT with four fully functioning ORs, a post-anesthesia care unit (PACU) with four beds, and an intensive care unit (ICU) with eight beds. There are elective procedures scheduled five days a week; surgical procedures two days a week, gynecological and obstetrics, including elective C/S, two days a week, and orthopedic and trauma operations two days a week. The Gedio zone and neighboring areas of SNNPR, Sidama region, and Oromia region have millions of residents who use the referral and teaching hospital.

Hawassa University Comprehensive and Specialized Hospital in Hawassa, situated in southwestern part of Hawassa city, the capital of Sidama, is situated 275 kilometers (km) south of Addis Ababa. In the Southern Nations, Nationalities, and People Region (SNNPR) and the nearby Oromia area, the tertiary Hawassa University Referral Hospital (HURTH) provides medical care for almost 12 million people. An operating room, intensive care unit (ICU), 16 wards with 400 beds, and 11 floors make up this hospital.

4.2. Study design

A multi-centered, randomized, controlled, single-blinded trial will be conducted at Dilla University General and Teaching Hospital and Hawassa University Comprehensive and Specialized Hospital.

4.3. Population

4.3.1. Source population

All patients undergoing elective gynecologic surgery under general anesthesia at Dilla University General and Teaching Hospital and Hawassa University Comprehensive and Specialized Hospital.

4.3.2. Study population

Adult patients between the ages of 18 and 65 undergoing elective gynecologic surgery under general anesthesia at Dilla University General and Teaching Hospital and Hawassa University Comprehensive and Specialized Hospital during the study period.

4.4. Inclusion and exclusion criteria

4.4.1. Inclusion criteria

ASA I and II patients between the ages of 18 and 65 undergoing elective gynecologic surgery at Hawassa University Comprehensive and Specialized Hospital and Dilla University Teaching Hospital under general anesthesia between April 10, 2023, and October 10, 2023, and gave informed consent.

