4.5. Sampling procedure and sample size

The sample size (N) was calculated by the formula for a continuous outcome variable with equal sample sizes in both groups, $n = 2[(Z_{\alpha}/2 + Z(1-\beta))^2 * \sigma^2]/(d^2)$ by G-power calculator. We assumed: significance level ($Z_{\alpha}/2$) = 0.05, taken 1.96, and power of study $Z(1-\beta)$ = 0.80, taken 0.84; σ^2 is the standard deviation taken from a previous study in South Korea⁴⁸, which is 1.9. Assuming a medium effect size in the OFA group compared to those receiving fentanyl is clinically significant, the calculated sample size for each group is 31, resulting in 62 participants in both groups. To account for potential contingencies, an additional 10% is added to the final sample size, resulting in 70 participants.

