4.6. Random sequence generation

The eligible participants presenting for gynecologic surgery at both study areas during the study period will be selected. Participants will be allocated to study groups by a computer-generated random allocation sequence number created by an independent anesthetist with a 1:1 allocation to the treatment group (T) and control group (C) the night before surgery.

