4.8.2. Independent variables

- Age
- Height
- Weight
- ASA physical status
- BMI
- Educational background
- Marital status
- Anesthetic experience
- Type of diagnosis and procedure
- Participants' hemoglobin and hematocrit
- Preoperative hemodynamic variables

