4.12. Data Processing and Analysis Procedure

After every data collection night, inconsistencies in data collection will be examined and fixed. Epi. Info version 7.2 will used for data entry and Statistical Package for the Social Sciences (SPSS) version 27will be used for data analysis.

The normality of data distributions for quantitative variables will be assessed using the Kolmogorov-Smirnov test and Levene's test will be used to check the homogeneity of variance. The plot of the Box will be used to check outliers. Histograms and visual inspection of individual data will be used to verify the data distribution.

Independent t-tests and ANOVA tests will be used to assess continuous data on pain severity at different postoperative times, and results will be presented as mean plus standard deviation. The categorical data of PONV at different postoperative times will be analyzed by chi-square or Fisher exact test and presented as frequencies, percentages, and a bar chart graphically. P-values of less than 0.05 will be determined as statistically significant.

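### Procedure type is listed as a variable but given no stated role in allocation or in the pain analysis, so the comparison of 35 per arm gives up precision and is exposed to chance imbalance

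*Combined protocol and SAP*

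**What the plan says.** Eligibility is broad. Section 4.3.1 defines the source population as "All patients undergoing elective gynecologic surgery under general anesthesia at Dilla University General and Teaching Hospital" and the Hawassa hospital. Section 4.4.1 admits "ASA I and II patients between the ages of 18 and 65 undergoing elective gynecologic surgery at Hawassa University Comprehensive and Specialized Hospital" or at the Dilla hospital, and goes on to require general anesthesia and consent. The exclusions in section 4.4.2 concern the patient or planned postoperative ventilation. None concerns the operation, the surgical approach or the expected duration.

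Section 4.8.2 includes "Type of diagnosis and procedure" among the independent variables, so the information is meant to be collected.

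Section 4.6 describes a "computer-generated random allocation sequence number created by an independent anesthetist with a 1:1 allocation". It mentions no strata, blocks or minimisation.

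For the outcome, the Executive Summary states: "The primary dependent variable is the pain severity measured by a visual analog scale postoperatively at discharge from the post-anesthesia care unit", and then at 6, 12 and 24 hours. Section 4.12 says that "Independent t-tests and ANOVA tests will be used to assess continuous data on pain severity at different postoperative times". It names no factor, covariate or adjusted model.

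**The concern.** The extent of surgery is a plausible driver of pain over the first 24 hours. It also affects how much of each regimen a patient receives: under section 4.10 the repeat lidocaine and fentanyl doses continue until skin closure begins, and ketamine runs as an infusion, so exposure follows operating time.

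If pain differs between operations, that variation sits in the error term of an unadjusted comparison and widens the confidence interval. With about 35 patients per arm and no stratification, one arm can also receive noticeably more of the painful operations by chance. The observed difference is then harder to interpret, and whether to adjust becomes a decision taken after the data are seen.

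At stake are power and the credibility of the primary result in a small trial.

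**Working it through.** **Inputs from the documents (section 4.5).** SD 1.9; power 80%; significance level "0.05, taken 1.96", which is two-sided; 31 per group, raised by 10% to 70 in total, or 35 per arm. The effect is called medium and no number is given.

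**Inputs assumed.** The documents give neither the mix of operations nor the pain gap between them. I take two classes, one holding a share p of 20–50% of patients, with mean VAS differing by D = 1–2 cm.

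**The plan's own figure.** With a medium effect read as 0.5 SD (an assumption), the formula in section 4.5 gives n = 2 × (1.96 + 0.84)² / 0.5² = 15.68 / 0.25 = 62.7, or 63 per group. The stated 31 is not reproduced; it appears if the factor 2 is left out (7.84 / 0.25 = 31.4). That is a separate matter. Here it means that power must be shown at two effects:

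- the effect that 31 per arm detects with 80% power in a two-sided t-test: 0.723 SD, or 0.723 × 1.9 = 1.37 cm;
- 0.5 SD, or 0.95 cm.

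With 35 per arm, t-test power is 84.7% at the first and 54% at the second.

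**Precision gained by adjustment.** Treat 1.9 as the total SD, so that it already contains the variation between procedures. The share of variance explained by class is R² = p(1 − p)D² / 1.9², with 1.9² = 3.61. The standard error is multiplied by √(1 − R²).

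| p | D (cm) | R² | SE ratio | Power at 1.37 cm | Power at 0.5 SD |
|---|---|---|---|---|---|
| none used | – | 0 | 1 | 84.7% | 54% |
| 0.2 | 1 | 0.16 / 3.61 = 0.044 | 0.978 | 86.2% | 56% |
| 0.3 | 1.5 | 0.4725 / 3.61 = 0.131 | 0.932 | 89.2% | 60% |
| 0.5 | 2 | 1.00 / 3.61 = 0.277 | 0.850 | 93.9% | 68% |

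The first and last assumed rows are the ends of the range. The loss of one degree of freedom does not change these figures at the precision shown.

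**Chance imbalance.** With independent assignment and 35 per arm, the number of patients in the class is Binomial(35, p) in each arm. A gap of 20 percentage points is 7 patients out of 35. The exact probability that the two counts differ by 7 or more is:

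- p = 0.2: 5.1%
- p = 0.3: 8.9%
- p = 0.5: 12.0%

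A gap of exactly 20 points shifts the unadjusted difference by 0.20 × D, that is 0.2 cm at D = 1 and 0.4 cm at D = 2. Against 1.37 cm these are 15% and 29% of the effect.

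**The case against.** **Randomization already deals with this.** In part it does. It rules out systematic bias, and the standard error of the t-test already allows for chance imbalance. A reader might infer that the primary result would be biased or the test invalid; the documents do not support that. Randomization does not recover the precision that a prognostic factor could give.

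**The SD may already cover the mix.** It may. A reader might infer that 1.9 ignores the variety of operations. Section 4.5 says only that it comes from a previous study in South Korea and does not describe the patients or operations, so that inference cannot be made. The calculation treats 1.9 as the total SD.

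**The gain is modest and assumed.** This stands. At a 1 cm gap and a 20% share, power at 1.37 cm rises by only 1.5 points, and the starting figure is already above the planned 80%. The 94% needs both a 50% share and a 2 cm gap. Section 4.10 describes intubation, a urinary catheter and 24-hour follow-up, so a large share of minor operations is uncertain. If nearly all cases fall in one class, adjustment gains little. The unsupported sample size is the larger problem.

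**Procedure might still be used.** The ANOVA in section 4.12 has no named factors, and section 4.8.2 calls procedure an independent variable. The accurate statement is therefore that no use is stated, not that procedure is excluded from the analysis.

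**Broad eligibility is legitimate.** Agreed. It is not a defect, and nothing here asks for it to be narrowed.

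**Conclusion.** The point holds as one of efficiency and prespecification, not of validity. The plan collects a variable likely to predict pain and states no role for it in allocation or analysis.

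The benefit of using it ranges from slight to material. It depends wholly on the assumed class share, the assumed pain gap and 1.9 being the total SD. The power figures also depend on the true effect: 1.37 cm is back-solved from 31 per arm, while 0.5 SD is one conventional reading of the stated medium effect. Under that smaller effect, adjustment helps but does not bring power to 80%.

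The change is worth making because it is nearly free and settles in advance how an imbalance would be handled.

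**What to change.** - **Eligibility (4.4):** leave unchanged.
- **Data collection (4.10):** record the planned operation before allocation in a small number of prespecified classes, for example open abdominal versus all other. The investigators should choose classes that separate their expected cases by extent of surgery.
- **Analysis (4.12):** include that class as a factor in the primary between-arm VAS comparison, using a linear model or two-way ANOVA, and report the number in each class by arm.
- **Allocation (4.6), optional:** have the independent anesthetist generate the list in blocks within class.

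The cost is one degree of freedom with two classes (one fewer than the number of classes in general), and the discipline of fixing the class before allocation. The variable is already to be collected, and SPSS, the planned software, can fit the model.
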